### **Project Proposal, Phase 3, Aim 3**

To test our hypotheses as described above, we propose to conduct an assessor - blinded RCT comparing the BESST intervention plus standard care to standard care alone. We will enroll up to 25 patients who are 18 years or older and are being discharged from a VA-CCN mental health treatment setting. The primary aim is to determine whether the BESST intervention reduces suicidal ideation at one and three months after discharge. The secondary aim is to evaluate the impact of the BESST intervention on other related measures of suicide risk including hopelessness, social connectedness, fatal/non-fatal suicide attempts and treatment engagement.

**Randomization:** Prior to the start of study enrollment, the study team otherwise not involved in recruitment will independently prepare allocation cards using a permuted block schedule. The same study staff member will then put these prepared allocation cards into sealed, opaque, numbered envelopes. After obtaining consent and completing the baseline assessment (see description below), the study staff member will take the next numbered envelope from the box (described above) and open the envelope to determine the patient's assignment. In the event that the patient has been assigned to the intervention, the study staff will notify the intervention staff in order that the intervention staff can initiate the intervention. Otherwise, the patient will be informed that they have been assigned to usual care.

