**Baseline Characteristics:** We will collect socio-demographic data from the electronic medical record such as age, sex, marital status and service history (e.g., branch, era, combat exposure). We will also collect diagnostic information using either the MINI International Neuropsychiatric Interview (MINI), which has been validated against the Structured Clinical Interview for Diagnostic and Statistical Manual of Mental Disorders (DSM). The MINI is a short, structured diagnostic interview that, on average, takes about 15 minutes to administer. We will ask about any history of suicide attempts using the validated Columbia Suicide Severity Rating-Scale (C-SSRS). The C-SSRS includes a seven-item subscale that assesses for actual and interrupted suicide attempts.

**Primary Outcome (Suicidal Ideation):** The primary outcome will be assessed using the Beck Scale for Suicidal Ideation (BSS) (Specific Aim 1). Patients will be asked about their current suicidal ideation (i.e., past week) at baseline and at the one-month and three-month follow-up

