## Research Protocol/Protocol Addendum Template

behaviors. The scale asks the assessor to document the actual and potential lethality of these behaviors. The C-SSRS is widely used in the VA.

**Secondary Outcome (Substance use):** We will assess substance use at baseline and follow-up assessments using a timeline follow-back approach. This method is commonly used in research studies to assess substance use patterns.

**Study Design:** As shown in **Figure 3** below, patients allocated to the BESST intervention will meet with the intervention staff around the time of discharge. During this visit, the patients will receive a brief educational intervention. Depending on patient preference, this visit will occur over the phone (or VA Video Connect). Depending on patient preference, the regular contacts will occur in a private office on the WRJ VAMC campus, or the contacts will occur over the phone (or VA Video Connect).

**Figure 3.** Schedule of Assessments and Interventions.

BIC= VA Brief Intervention and Contact Program; D/C = discharge; dy = days; m = months; MH = Mental Health; T0, T1, T2 = assessment time points; wk = weeks

All patients (including patients randomized to the intervention) will have access to standard care. Furthermore, regardless of study assignment, all patients will undergo outcome assessment at baseline (0M), one month (1M), and three months (3M). These assessments will be conducted by the independent outcome assessor. We anticipate that, in most cases, the baseline assessment will occur around the time of discharge. However, because patients will be recruited remotely, we anticipate that the baseline assessments may in some cases happen a few weeks after discharge. Depending on patient preference, the independent outcome assessor will conduct the follow-up assessments in a private office on the WRJ VAMC campus, over the phone, or using VA Video Connect. The assessors will be blinded to study assignment and the patients will be instructed to not reveal their status to the assessor.

Because we are recruiting patients from a large geographic area (New Hampshire, Maine and Vermont), we anticipate that several enrolled patients will prefer phone (or VA Video Connect) over in-person follow-up. Fortunately, the assessment instruments that we selected for this study can be administered over the phone or in person.

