## Research Protocol/Protocol Addendum Template

---

secondary aims of interest of this study. We will assess for statistically significant differences in baseline study characteristics such as age, sex, race, and mental health diagnosis, between study arms using *t*-tests for continuous measures and chi-squared tests for dichotomous variables. We will report these results using 95% confidence intervals (CI) and *P*-values. We will define statistical significance as a *P*-value < 0.05.

**Specific Aim 1:** We will generate descriptive summary statistics (e.g., means and standard errors, medians) and graphical displays for the BSS total scores at baseline and at each of the follow-up assessments. In the case of the pilot study of the BESST intervention in up to six patients, we will use a repeated measures analysis of variance (ANOVA) test to assess for changes in continuous variables in the first three months after discharge. Second, if the repeated measures ANOVA suggested a significant difference in means across time, we will perform a post-hoc, pair-wise comparison of means at baseline and at each follow-up using a two-sample *t*-test.

With regards to the RCT of the BESST intervention, we will use a generalized linear mixed model to assess for changes in continuous variables in the first three months after discharge. We will consider allocation of study arm (categorical measure) and time (continuous measure) as fixed effects. Random effect will be used to account for correlation that arises from repeated measures of the same individual. We will assume a linear effect and model changes in suicidal ideation over time. We will calculate 95% CI and *P*-values and will define a *P*-value of < 0.05 to be statistically significant. We will use the maximum likelihood ratio to account for any missing data. Based on available evidence, we hypothesize that the BESST intervention plus standard care will lead to a significant reduction in suicidal ideation after discharge.

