**Specific Aim 2:** We will generate descriptive summary statistics (e.g., means and standard errors, medians) and graphical displays for our secondary outcomes of interest at baseline and at each of the follow-up assessments. In the case of the pilot study of the BESST intervention in up to six patients, we will use a repeated measures analysis of variance (ANOVA) test to assess for changes in continuous variables in the first three months after discharge. Second, if the repeated measures ANOVA suggested a significant difference in means across time, we will perform a post-hoc, pair-wise comparison of means at baseline and at each follow-up using a two-sample *t*-test.

With regards to the RCT of the BESST intervention, we will use a generalized linear mixed model to assess for changes in continuous variables in the first three months after discharge. We will calculate the associated 95% confidence intervals and *P*-values. As with the BSS, we will consider allocation of study arm (categorical measure) and time (continuous measure) as fixed effects. Random effect will be used to account for correlation that arises from repeated measures of the same individual. We will assume a linear effect and model changes in suicidal ideation over time. We will define a *P*-value of < 0.05 to be statistically significant. We will use the maximum likelihood ratio to account for any missing data. Based on available evidence, we hypothesize that the BESST intervention plus standard care will lead to a significant reduction in our secondary outcomes after discharge.

For the categorical measure of healthcare utilization, we will use chi-squared tests to compare findings between study arms.

**Specific Aim 3:** We will not be powered to detect a statistically significant difference between study arms with regards to suicide deaths and suicide attempts. These events are very difficult to examine in a clinical trial. A study would need to recruit well over 1,000 patients. Because we assume that few events will be observed in either arm, we plan to summarize our results by

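### The RCT model specifies no adjustment for baseline score, although every scale is measured before allocation; in a trial of at most 25 patients this leaves chance imbalance in the arm estimate and gives up precision

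*Combined protocol and SAP*

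**What the plan says.** All references are to the combined protocol and SAP, Project Proposal, Phase 3, Aim 3.

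- **Statistical Analyses, Specific Aim 1 (BSS).** The fixed effects for the RCT are given in one sentence: "We will consider allocation of study arm (categorical measure) and time (continuous measure) as fixed effects". Two sentences complete the model: "Random effect will be used to account for correlation that arises from repeated measures of the same individual" and "We will assume a linear effect and model changes in suicidal ideation over time".
- **Statistical Analyses, Specific Aim 2 (secondary scales).** The same form is carried over: "As with the BSS, we will consider allocation of study arm (categorical measure) and time (continuous measure) as fixed effects".
- **Primary Outcome and Study Design.** "Patients will be asked about their current suicidal ideation (i.e., past week) at baseline and at the one-month and three-month follow-up" assessments, and "all patients will undergo outcome assessment at baseline (0M), one month (1M), and three months (3M"). Table 2 schedules every scale at month 0.
- **Randomization.** Baseline comes before allocation: "After obtaining consent and completing the baseline assessment (see description below), the study staff member will take the next numbered envelope". The schedule uses permuted blocks. Ratio, block size and stratification are not mentioned.
- **Statistical Analyses, opening paragraph.** The only stated response to baseline differences is testing: "We will assess for statistically significant differences in baseline study characteristics such as age, sex, race, and mental health diagnosis, between study arms". No adjustment follows from these tests.

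No section makes the baseline score a covariate or constrains the arms to share a baseline mean.

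**The concern.** Because the baseline scales are completed before the envelope is opened, any difference between arms at baseline is chance. The baseline score usually predicts the follow-up score. An analysis that does not condition on it therefore lets part of the chance difference into the arm estimate, and leaves in the error term variation that the trial has already measured.

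In a large trial this would be minor. With about 12 patients per arm, a sizeable baseline difference is quite likely. The plan also leaves open whether an adjusted or unadjusted result would be reported once an imbalance had been seen.

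**Working it through.** **No plan figure to reproduce.** The Sample Size section gives up to 25 patients and a within-group change of more than five BSS points from an earlier pilot. It gives no SD, correlation, between-arm difference or power value.

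**Inputs.** From the documents: N up to 25; visits at 0, 1 and 3 months; fixed effects arm and continuous time; a subject random effect of unstated structure. Assumed: 1:1 allocation (12 v 13), a normal linear mixed model with random intercept, equal SDs, equal correlation r = 0.3, 0.5 or 0.7 between any two visits, and complete data.

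**1. Size of chance imbalance.** The SE of a difference in baseline means is sqrt(1/12 + 1/13) = 0.400 SD. P(|difference| ≥ 0.5 SD) = 2[1 - Φ(0.5/0.400)] = 21%.

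**2. Share of a baseline difference b that reaches the arm estimate.** With no true effect, the expected follow-up difference given b is r·b at each visit.

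- *Arm + time over three visits.* The arm term is the difference in the mean of the three visits: (1 + 2r)/3.
- *Linear arm-by-time added, contrast at 3 months.* With times 0, 1, 3, the slope difference times 3 has weights -6/7, -3/14 and 15/14. The share is -6/7 + r(12/14) = -(6/7)(1 - r).
- *Months 1 and 3 only, unadjusted.* The share is r.
- *Baseline as covariate, or common baseline mean.* The share is 0.

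| Model | r = 0.3 | r = 0.5 | r = 0.7 |
|---|---|---|---|
| Arm + time, three visits | +53% | +67% | +80% |
| Linear arm-by-time added | -60% | -43% | -26% |
| Months 1 and 3 only | +30% | +50% | +70% |
| Baseline-adjusted | 0% | 0% | 0% |

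The sign reverses in the second row because of regression to the mean: the arm that starts higher tends to fall further.

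**3. Precision.** Variances are in SD² units, before the common factor (1/12 + 1/13).

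- *3-month contrast, linear arm-by-time model.* Unconstrained: 9(1 - r)/(14/3) = 27(1 - r)/14, which is 1.350, 0.964 and 0.579. With a common baseline mean: 9(1 - r)(1 + 2r)/(10 + 4r), which is 0.900, 0.750 and 0.506. The reductions are 33%, 22% and 12.5%, before any small-sample cost. At r = 0.5 the SE falls from 0.393 to 0.347 SD.
- *Mean of the 1- and 3-month differences.* Unadjusted: (1 + r)/2 = 0.650, 0.750 and 0.850. Adjusted: [(1 + r)/2 - r²] × (1 + 1/21) = 0.587, 0.524 and 0.377. The reductions are 10%, 30% and 56%, net of the covariate's degree of freedom.

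The two comparisons move in opposite directions with r, so neither set of percentages should be quoted without its comparator.

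**The case against.** Several objections carry weight.

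- **Chance imbalance is not bias.** A reader might infer that the planned analysis is biased towards or against the intervention. Nothing supports that. Over repeated randomisations the imbalance averages to zero, and the SE and P-value of a correctly specified unadjusted model already allow for it. What remains is accuracy given the imbalance that occurs, and efficiency.
- **Baseline as a modelled visit is inferred.** The plan never says outright that the month-0 score is a response in the mixed model. The inference comes from its listing among the outcome assessments and from modelling change over time. If only months 1 and 3 are modelled, the gap is still there, as the third row of the table shows.
- **The precision gain is not measured against the stated model.** A reader might take the 10/30/56% as savings over the plan's own arm term. They are not. That term's variance is (1 + 2r)/3 = 0.533, 0.667 and 0.800. Against the adjusted 0.587, 0.524 and 0.377, the change is +10%, -21% and -53%. Even that compares different quantities, because the stated arm term averages in a pre-treatment visit.
- **The missing arm-by-time term matters too.** It is a separate gap, but it changes the sign and size of the carry-through. Adding it alone does not bring the share to zero.
- **Absence of stratification is silence.** The Randomization paragraph describes none; it does not rule it out.

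**Conclusion.** The point holds as a recommendation on efficiency and conditional accuracy. The plan specifies no baseline adjustment for the BSS or the secondary scales, and each reading of the model considered here lets some chance imbalance through: from +80% to -60% of the difference for r between 0.3 and 0.7, against none with adjustment. With 12 v 13 patients a difference of at least 0.5 SD has a 21% chance of arising on any one scale.

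The precision gain depends on r and on the comparator: 33/22/12.5% of variance against a linear arm-by-time model, or 10/30/56% against an unadjusted follow-up mean, at r = 0.3/0.5/0.7. The gain is small if r is near 0.3 and the comparison is follow-up only. All of these sizes rest on the assumed 1:1 allocation, full enrolment, equal SDs, equal correlations and complete data. The documents do not support a claim of systematic bias, or a single figure for precision lost under the model as stated.

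**What to change.** In Statistical Analyses, Specific Aim 1, replace the fixed-effects sentence for the RCT with one of the following.

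- **Covariate version.** Model the 1-month and 3-month BSS with baseline BSS as a covariate, plus arm, visit and arm-by-visit.
- **Common-baseline version.** Keep all three visits, give both arms one baseline mean, and include arm-by-visit terms at months 1 and 3. The constraint cannot be combined with arm and time main effects alone, because it would then force the arm effect to zero. This version also keeps patients who have baseline data only, whereas the covariate version drops them.

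In Specific Aim 2, do the same for each secondary scale with its own baseline. State which adjusted contrast is the primary result, so that the choice is fixed before any imbalance is seen.

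The cost is a short rewrite of two paragraphs and about one degree of freedom, roughly 5% of variance (1/21). No added data, visits or patients are needed.

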## Research Protocol/Protocol Addendum Template

**Hypothesis:** We will develop a reliable method to incorporate VA BIC into care processes for rural patients discharged from VA-CCN mental health treatment settings. The adaptation will be called the Building VA Engagement, Self-efficacy, and Social Support To Prevent Suicide (BESST) intervention.

**Aim 2:** During phase 2, we will pilot test the BESST intervention in four to six rural patients who are referred to (and discharged from) a VA-CCN mental health treatment setting.

**Hypothesis:** We will obtain data on the feasibility of studying the BESST intervention in rural patients who are referred to (and discharged from) a VA-CCN mental health treatment setting. We will identify any further modifications that may be required prior to studying BESST in this population.

**Aim 3:** During phase 3, we will conduct a randomized trial of the BESST intervention versus usual care in rural patients who are referred to (and discharged from) VA-CCN mental health treatment settings. We aim to determine whether the BESST intervention can improve suicide-related outcomes in this population.

**Hypothesis:** We will determine whether the BESST intervention reduces suicidal ideation and hopelessness and improves social connectedness and treatment engagement in rural patients who are referred to (and discharged from) VA-CCN mental health treatment settings.

**Note:** As shown in **Table 1**, we will develop a reliable method to incorporate our VA BIC intervention into care processes for rural patients who are discharged from VA-CCN mental health treatment settings.

**Table 1:** Proposed phases of study of the BESST intervention in rural patients.

Phase	Aim	Proposed study activities during phase of work
Phase One	Aim 1	

• Recruit three rural VA facilities and their affiliated VA-CCN sites.

• Use an interview guide to interview site staff about current VA-CCN processes of care and to determine a reliable method to incorporate VA BIC into these processes. The adaptation will be called BESST.

Phase Two	Aim 2	

• Pilot study of BESST in 4 – 6 patients who access VA-CCN care.

• Finalize the BESST manual.

Phase Three	Aim 3	

• Use results of Phase 1 and 2 to inform the design of a pilot, randomized trial of the BESST intervention for VA-CCN mental health settings.

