## Research Protocol/Protocol Addendum Template

---

Finally, we will conduct a randomized trial of the BESST intervention versus usual care in rural patients who are referred to (and discharged from) VA-CCN mental health treatment settings. The results of our work will ultimately lead to the development of a key resource for rural VA facilities to use to keep patients who are referred to (and discharged from) VA-CCN mental health treatment settings involved in VA care and to prevent death by suicide.

**Note we report here only on the portion of the protocol that relates to the pilot RCT that is registered at clinicaltrials.gov at the number listed on the first page. Thus, pages 6-12 are intentionally excluded from the document as they pertain only to aims 1 and 2 of the larger project.**

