## Research Protocol/Protocol Addendum Template

---

assessments. The BSS is a self-reported questionnaire that assesses severity of suicidal ideation. The BSS measures attitudes, behaviors, and plans to die by suicide. Each item on the BSS is scored on a scale from 0 to 2 and the first 19 of the 21 items are used to calculate a total score ranging from 0 – 38. The BSS has high reliability and is a valid measure of suicidal ideation. The BSS may be a measure of risk of suicide. There is evidence that the BSS is measurement invariant across time.

**Secondary Outcome (Patient Engagement):** We will measure patient engagement in treatment at baseline and at follow-up assessments in two ways. First, we will examine healthcare utilization in the first three months after discharge. We will look at the amount of contact with mental health providers as well as the time to first mental health appointment after discharge. We will also evaluate evidence of disruptions of care such as no-show and cancelled appointments. We will abstract these measures from the electronic medical record. Since it is possible that some patients may receive portions of their care outside of the VA system, we will also ask patients to self-report on non-VA care. To gather data regarding the patient's sense of self-efficacy around managing their suicide risk after discharge, we will administer the validated Suicide-Related Coping Scale (SRCS). This SRCS includes 17 questions related to a patient's perception of their ability to cope with suicidal thoughts. Each item is assessed using a 5-point Likert scale and the measure has been developed based on two studies of suicide prevention strategies conducted within Veteran populations. The scale includes two subscales including an External Coping subscale and an Internal Coping Subscale. Both subscales have shown good acceptable internal consistency. The two factors are also sensitive to change over time. Higher scores on the scale suggest better coping. In addition to the SRCS, we will also measure the patient's general sense of self-efficacy using the General Self-Efficacy Scale (GSE). This is a valid scale of self-efficacy that is designed for the general population (12 years or older) and it has been tested in various countries.

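### Phase 2 pilot only: the post-hoc test treats baseline and follow-up of the same four to six patients as independent samples; a paired t-test is needed (minor). Lesser RCT point: no stated test suits time to first appointment.

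*Combined protocol and SAP*

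**What the plan says.** Phase 2 is a single cohort: Aim 2 states that "we will pilot test the BESST intervention in four to six rural patients". Under Statistical Analyses, Specific Aim 1 (the Beck Scale for Suicidal Ideation) and Specific Aim 2 (secondary outcomes) give this cohort the same two steps. The first is a repeated measures ANOVA over the visits. If it is significant, the second is a "pair-wise comparison of means at baseline and at each follow-up using a two-sample" t-test. The note at the end of Preliminary Studies limits the document, saying that "we report here only on the portion of the protocol that relates to the pilot RCT", but both sentences remain in the current statistical text.

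For the RCT, Secondary Outcome (Patient Engagement) sets the window: "we will examine healthcare utilization in the first three months after discharge". Within it, "We will look at the amount of contact with mental health providers as well as the time to first mental health appointment after discharge". Specific Aim 2 of Statistical Analyses promises summaries and "graphical displays for our secondary outcomes of interest at baseline and at each of the follow-up assessments". It then names two inferential methods. One is a mixed model for changes in continuous variables, with arm and linear time as fixed effects and a random effect for repeated measures. The other reads: "For the categorical measure of healthcare utilization, we will use chi-squared tests to compare findings between study arms". The categorical measure is not defined, and no survival method or censoring rule is given.

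**The concern.** A two-sample t-test assumes that the two sets of values are independent. Here they are two visits by the same people, and the cohort has no second group. The ANOVA that triggers the test respects this structure; the test that follows drops it. The word pair-wise refers to pairs of visits and does not make the test paired. At stake are P-values that are too large and intervals that are usually too wide for the pilot's changes over time, in a cohort so small that little power can be spared.

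In the RCT, time to first appointment gives one number per patient, and for anyone not seen within three months that number is only known to exceed the window. A model of slopes over repeated visits has nothing to work on. Chi-squared works only after the time is cut into categories, which discards when the patient was seen. A definition is also missing. BESST may be delivered by mental health staff (BESST Intervention Description) and comprises one education visit and seven contacts (Therapeutic Risks), so 1 + 7 = 8 sessions in one arm only. The engagement section does not say whether these count as provider contacts or as the first appointment.

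**Working it through.** The plan states no figure for either analysis, so there is none to reproduce.

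**Pilot.** From the documents: 4 to 6 patients, three visits, significance at P < 0.05. Assumed: two-sided tests, normal scores with equal variances, equal correlation ρ between visits, and a 1 SD change at both follow-ups.

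The variance of the mean change is 2σ²(1 − ρ)/n, but the two-sample test uses about 2σ²/n. Its standard error is therefore too large by 1/√(1 − ρ):

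- ρ = 0.3: 1/√0.7 = 1.20
- ρ = 0.5: 1/√0.5 = 1.41
- ρ = 0.7: 1/√0.3 = 1.83

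Against this, the two-sample test has 2n − 2 degrees of freedom and the paired test n − 1: 10 v 5 at n = 6, and 6 v 3 at n = 4. At low correlation the extra degrees of freedom offset the inflated standard error.

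Simulation (200,000 cohorts per setting) gives the net effect. Power is shown as two-sample v paired. The last column requires a significant ANOVA first, as the plan does.

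| n | ρ | True size, two-sample | Power, t-test alone | Power, ANOVA required first |
|---|---|---|---|---|
| 6 | 0.3 | 2.5% | 33% v 39% | 27% v 31% |
| 6 | 0.5 | 1.2% | 32% v 51% | 28% v 44% |
| 6 | 0.7 | 0.4% | 31% v 72% | 30% v 67% |
| 4 | 0.3 | 2.8% | 20% v 22% | 13% v 15% |
| 4 | 0.5 | 1.6% | 19% v 29% | 14% v 21% |

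The paired test used alone holds its size at about 5% throughout. At ρ = 0 and n = 6 the two-sample test has slightly more power (35% v 29%, t-test alone). At ρ of about 0.2 the two tests are practically equal. Intervals behave likewise: at n = 4 and ρ = 0.3 the average half-width is 1.65 SD two-sample and 1.73 SD paired.

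**RCT, time to first appointment.** From the documents: up to 25 patients and a three-month window. Assumed: 13 v 12 patients, a 90-day window, exponential times from discharge, and a hazard ratio of 2.5 in favour of BESST. The documents give no attendance figure, so the share p of controls seen by day 90 is varied. The share seen in the BESST arm is then 1 − (1 − p)^2.5; for p = 0.50, 1 − 0.5^2.5 = 82%.

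| Controls seen | BESST arm seen | Log-rank power | Day-90 yes/no chi-squared power |
|---|---|---|---|
| 29% | 58% | about 30% | 28% |
| 50% | 82% | 45% | 42% |
| 75% | 97% | 56% | 27% |
| 87% | 99% | 57% | 5% |

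With few patients seen, yes/no holds nearly all the information and the log-rank test gains 2 to 3 points. Once nearly everyone in both arms is seen, yes/no has almost nothing left to compare, while the timing still differs.

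**The case against.** The pilot sentence lies outside the part of the project that the document sets out to report. Aim 2 is about feasibility, and nothing makes Phase 3 depend on a Phase 2 P-value. The error is conservative, and the largest gaps need six patients and a correlation near 0.7. All of this stands, and it is why the point is minor. It does not make the sentence right: it appears twice in the current text and names the wrong test for paired data.

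A reader might infer that the slip inflates false positives or reaches the trial's primary result. Neither follows. With positive correlation the size falls below 5%, and the RCT arms are compared by the mixed model.

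A reader might also infer that RCT patients who are never seen will be dropped. Under the same assumptions, a t-test on seen patients only would have 5% to 9% power when 29% to 50% of controls are seen. The plan nowhere proposes that analysis, so this cannot be counted as its loss. The mixed model is described for changes in continuous variables, utilization has its own sentence, and descriptive summaries are promised for every secondary outcome. What remains is that no suitable inferential method or censoring rule is named for this one measure.

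On the counting of sessions, the protocol calls those who deliver BESST intervention staff and speaks separately of mental health providers, which suggests that the sessions are not meant to count. It does not say so.

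**Conclusion.** The two-sample t-test is the wrong test for the Phase 2 cohort, in both places. The consequence is lost power and not false positives: with the ANOVA required first, 4 to 37 percentage points at six patients over correlations 0.3 to 0.7 (31 − 27 and 67 − 30), and 2 to 7 points at four patients over correlations 0.3 to 0.5 (15 − 13 and 21 − 14). There is no real loss at about 0.2 or below. The correlations and the 1 SD change are assumptions. No RCT result is touched. Severity: minor.

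The RCT point is a smaller gap in the plan for one secondary outcome. The gain from a log-rank test over a yes/no comparison depends on attendance, which the documents do not give: small when half or fewer of controls are seen, large when most are. A general claim that the gain is negligible, or that it is always large, is not supported.

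**What to change.** In Statistical Analyses, Specific Aims 1 and 2, replace the two-sample t-test with a paired t-test for the pilot cohort. This changes one word in each place.

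For the RCT, add to Specific Aim 2 that time from discharge to first mental health appointment will be shown as Kaplan-Meier curves and compared by a log-rank test, censoring at the end of the three-month window, withdrawal or death. State in the engagement outcome that BESST sessions count neither as contacts with mental health providers nor as the first appointment. This takes two or three sentences. The data come from the record abstraction already planned.

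A sensitivity analysis counted from randomisation is optional. Randomisation follows the baseline assessment, and Study Design expects that "in most cases, the baseline assessment will occur around the time of discharge", with a delay of a few weeks in some.
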